MMRM analyses and data is assumed to be missing at random (MAR). An unstructured covariance structure will be used to model the within-patient error. If the model with unstructured covariance structure doesn't converge, the compound symmetry structure will be used. Based on the MMRM model described above, treatment effects of CNTO 1959 groups versus placebo group at Week 16 will be estimated based on least-square (LS) means of the differences. The p-values for the LS mean differences along with the 2-sided 95% confident intervals (CIs) will be presented.

Major secondary endpoints of this study are not prospectively powered and all p-values reported for secondary endpoints will not adjust for multiple comparisons. Major secondary endpoints are:

- The change from baseline in PPSI through Week 16 will be analyzed using the same MMRM model as described for the primary analysis, except for including the baseline PPSI score, instead of baseline PPPASI score, as the covariate. Treatment effects of CNTO 1959 groups versus placebo group will be estimated based on least-square (LS) means of the differences. The p-values for the LS mean differences along with the 2-sided 95% CIs will be presented. The change from baseline in PPSI through Week 16 will also be summarized by treatment group and week using descriptive statistics.
- The proportion of subjects who achieve a PPPASI-50 at Week 16 will be compared between the CNTO 1959 treatment groups and placebo group using a CMH chi-square test stratified by baseline PPPASI total score (≤ 20 , 21-30, ≥ 31) and smoking status (smoking or non-smoking). The proportion through Week 16 will also be summarized by treatment group and week using frequencies and percentages with 95% CI.
- For other secondary endpoints (including exploratory endpoints), the continuous variables will be summarized by treatment group and week using descriptive statistics, which will include the number of subjects (N), mean, SD, median, minimum, and maximum and the measurements through Week 16 will be analyzed using an MMRM model where there are repeated measurements; or an analysis of variance model based on appropriate rank scores or ANCOVA model where there is no repeated measurement. The categorical variables will be summarized by treatment group and week using frequencies and percentages. The binary variables through Week 16 will be compared using stratified CMH chi-square test or Fisher's exact test.

Pharmacokinetic

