11.2. Sample Size Determination

This study is designed to evaluate the efficacy of CNTO 1959 versus placebo in subjects with palmoplantar pustulosis at Week 16. Palmoplantar Pustulosis Area and Severity Index (PPPASI) total score will be used in this study as the primary variable. A fixed-sequence testing procedure, starting with the high dose group (CNTO 1959 200 mg), will be used to control the overall Type I error rate at the 0.05 level (2-sided) for comparisons of the 2 CNTO 1959 treatment groups with the placebo group.

The sample size was chosen to achieve at least 90% power to detect treatment difference between CNTO 1959 groups and placebo for the primary endpoint at a significance level of 0.05 (2-sided).

The assumptions for the sample size and power calculations came from the results of a phase 2 study in subjects with PPP (CNTO1959PPP2001):

Table 1: Change from baseline in PPPASI score at Week 16 in CNTO1959PPP2001 study

	Placebo	CNTO1959 200 mg
n	24	25
Mean \pm SD	-6.40 \pm 7.545	-10.24 \pm 8.072
LS mean ^a	-5.47	-11.12
LS mean difference (SE) (versus Placebo) ^a	-5.65 (2.061)	
95% CI for difference in LS mean (versus Placebo) ^a	(-9.80, -1.50)	
p-value (versus Placebo) ^a	0.009	

a. Based on ANCOVA with treatment as a factor and baseline PPPASI total score as a covariate.

Since the baseline PPPASI total score in CNTO1959PPP2001 study is deemed unbalanced across the comparison groups due to its exclusion from stratification factors, LS-means should be able to provide fairer comparisons than would comparisons of the raw means and as a result, the assumed treatment effect size is based upon the LS mean difference. Assuming a 5.5 treatment effect for both CNTO 1959 groups and a common standard deviation (SD) of 8.1 in change from baseline in PPPASI score at Week 16, 47 subjects per group will provide statistical power of 90% for comparisons of CNTO 1959 200 mg versus placebo at a significance level of 0.05 (2-sided).

Table 2: Power for a fixed sample size (47 subjects/treatment) at alpha = 0.05 with different assumptions about the change from baseline in PPPASI score at Week 16

Difference	SD	Power
4.5	7.5	82%
	8.1	75%
	8.5	71%
5.0	7.5	89%
	8.1	84%
	8.5	80%
5.5	7.5	94%
	8.1	90%
	8.5	87%

Based on the two sample t-test with equal variances of Query Advisor. Release 7.0.

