11.3.3. Primary Analysis

Primary endpoint of this study is change from baseline in PPPASI total score at Week 16. In the primary efficacy analyses, data from all randomized subjects will be analyzed according to their assigned treatment group. In this primary analysis, the change from baseline in PPPASI total score through Week 16 will be analyzed using an MMRM with treatment (CNTO 1959 high dose, CNTO 1959 low dose, or placebo), smoking status (smoking or non-smoking), week (2, 4, 8, 12, 16), and treatment-by-week interaction as fixed effects and baseline PPPASI score as a covariate. Un-imputed data will be used for MMRM analyses and data is assumed to be missing at random (MAR). An unstructured covariance structure will be used to model the within-patient error. If the model with unstructured covariance structure doesn't converge, the compound symmetry structure will be used. Based on the MMRM model described above, treatment effects of CNTO 1959 groups versus placebo group at Week 16 will be estimated based on least-square (LS) means of the differences. The p-values for the LS mean differences along with the 2-sided 95% CIs will be presented.

Sensitivity analyses for primary endpoint (change from baseline in PPPASI total score at Week 16) will be performed using an ANCOVA model with treatment (CNTO 1959 high dose, CNTO 1959 low dose, or placebo) and smoking status (smoking or non-smoking) as factors and baseline PPPASI score as a covariate, based on the data with and without imputation of last observation carry forward (LOCF). The last available post-baseline PPPASI total score will be carried forward to impute the PPPASI total score that are missing after discontinuation of treatment up to Week 16 of the double-blind treatment period.

Furthermore, subgroup analyses will be performed to evaluate consistency of the primary endpoints over demographics and baseline disease characteristics as appropriate. The exploratory analyses for the primary endpoints to evaluate the dose-response may be performed if deemed appropriate. Additional efficacy analyses may also be performed and will be documented in the SAP.

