A fixed-sequence testing procedure will be used to control the overall Type I error rate at the 0.05 level for the primary endpoint. Specifically, the high dose group (i.e., CNTO 1959 200 mg) will first be compared with the placebo group at the 2-sided 0.05 level of significance. Only if this test is positive will the low dose group (i.e., CNTO 1959 100 mg) be compared with the placebo dose group at the 2-sided 0.05 level of significance.

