11.3.4. Major Secondary Analyses

Major secondary endpoints of this study are not prospectively powered and all p-values reported for secondary endpoints will not adjust for multiple comparisons. Major secondary analyses are:

- The change from baseline in PPSI through Week 16 will be analyzed using the same MMRM model as described for the primary analysis, except for including the baseline PPSI score, instead of baseline PPPASI score, as the covariate. Treatment effects of CNTO 1959 groups versus placebo group will be estimated based on least-square (LS) means of the differences. The p-values for the LS mean differences along with the 2-sided 95% CIs will be presented. The change from baseline in PPSI through Week 16 will also be summarized by treatment group and week using descriptive statistics.
- The proportion of subjects who achieve a PPPASI-50 at Week 16 will be compared between the CNTO 1959 treatment groups and placebo group using a CMH chi-square test stratified by baseline PPPASI total score (≤ 20 , 21-30, ≥ 31) and smoking status (smoking or non-smoking). The proportion through Week 16 will also be summarized by treatment group and week using frequencies and percentages with 95% CI.

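### The only fallback for the primary MMRM is plain compound symmetry, which understates the Week 16 standard error if residual variability grows over visits

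*Protocol*

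**What the plan says.** Section 11.3.3 of the Protocol models change from baseline in PPPASI with treatment, smoking status, "week (2, 4, 8, 12, 16), and treatment-by-week interaction as fixed effects and baseline PPPASI score as a covariate". For the covariance: "An unstructured covariance structure will be used to model the within-patient error". One fallback is named: "If the model with unstructured covariance structure doesn't converge, the compound symmetry structure will be used". The Synopsis (Statistical Methods, Efficacy) gives the same rule. No intermediate structure, heterogeneous structure or robust standard error is mentioned.

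The treatment contrast that counts is at Week 16 only. Section 11.3.3 also states: "A fixed-sequence testing procedure will be used to control the overall Type I error rate at the 0.05 level for the primary endpoint". Section 11.3.4 carries the model over to PPSI: "The change from baseline in PPSI through Week 16 will be analyzed using the same MMRM model as described for the primary analysis".

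A Week 16 ANCOVA, with and without LOCF, is planned as a sensitivity analysis. It is not the fallback for the primary test.

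**The concern.** Compound symmetry assumes the same residual variance at every visit. The model-based standard error of the Week 16 contrast then rests on a variance averaged over Weeks 2, 4, 8, 12 and 16. If the early visits are less variable than Week 16, that average is too small.

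A rise is plausible even without a drug effect. After adjustment for baseline, residual variance grows as a subject's score loses its correlation with baseline, and Week 2 is closer to baseline than Week 16 is. If the rise is present and the fallback is used, the two tests in the fixed sequence would not hold their stated 0.05 level.

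**Working it through.** **The plan's own figure.** Section 11.2 states 47 per group for 90% power (difference 5.5, SD 8.1, two-sided 0.05). The exact two-sample t calculation gives n = 47 and power 90.3%, so it reproduces.

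**Size of the error under compound symmetry (CS).** With complete data and residual SD s_t at visit t:

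- r = CS standard error / true standard error = sqrt(mean of s_t² over the five visits) / s_16
- actual two-sided Type I error = 2 × (1 − Φ(1.96 × r))

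**Anchor from Table 1 of section 11.2.** The protocol gives no SDs before Week 16, so the Phase 2 figures are used to limit the assumption.

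1. Pooled raw SD of change: sqrt((23 × 7.545² + 24 × 8.072²)/47) = 7.82.
2. The adjusted SE of 2.061 comes from a model described as: "Based on ANCOVA with treatment as a factor and baseline PPPASI total score as a covariate". The residual SD is therefore at most 2.061/sqrt(1/24 + 1/25) = 7.21.
3. Part of that SE reflects baseline imbalance. The raw difference is −10.24 + 6.40 = −3.84 and the adjusted one is −5.65, a shift of 1.81. Allowing for this brings the residual SD to about 7.0.
4. If score SDs are equal at baseline and Week 16, with correlation c, then residual variance / raw-change variance = (1 + c)/2. So (7.0/7.82)² ≈ 0.80 and c ≈ 0.6. The value 0.59 is used below. Without step 3, c = 0.70.

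**Assumed decay.** Correlation between weeks s and t is R × rho^|s − t|, with R × rho^16 = 0.59. R is the share of score variance that is not visit-to-visit measurement noise. R = 1.0 means all the lost correlation is gradual. R = 0.59 means it is all noise, and the residual SDs are flat.

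**Worked case, R = 1.0.** With the single baseline slope in the model, the residual SDs scaled to 7.0 at Week 16 are 3.30, 4.18, 5.42, 6.31 and 7.00. The mean square is 29.3, so r = sqrt(29.3)/7.0 = 0.773. Type I error is 2 × (1 − Φ(1.515)) = 0.130.

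**Check by fitted models.** The fits used three arms of 50, five visits, REML and 9–10% monotone MAR dropout under the null, with 6,000 runs per row (Monte Carlo error 0.003–0.004).

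| R | Closed form, CS | Fitted, CS | CS SE vs true |
|---|---|---|---|
| 1.0 | 0.130 | 0.125 | 1.14 vs 1.47 |
| 0.9 | 0.101 | 0.101 | 1.23 vs 1.47 |
| 0.8 | 0.079 | 0.080 | 1.31 vs 1.47 |
| 0.7 | 0.063 | 0.058 | 1.39 vs 1.45 |
| 0.59 (flat) | 0.050 | 0.048 | 1.47 vs 1.46 |

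The unstructured model gave 0.043–0.050 across these rows. At 75 per arm (3,000 runs), CS gave 0.132 for R = 1.0 and 0.094 for R = 0.8, against 0.051 and 0.058 unstructured.

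**Other assumptions.**

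- With c = 0.50 or 0.70 and R from 0.8 to 1.0, the closed form gives 0.068–0.137.
- Simple assumed profiles ending at SD 8.1 give a similar range: 6.5/7/7.5/7.8/8.1 gives 0.073 and 4/5/6.5/7.5/8.1 gives 0.121. For the second profile, a separate REML simulation of 480 trials gave 0.115 with CS and 0.056 unstructured.
- A falling profile (9.5/9.15/8.8/8.45/8.1) gives 0.033, which is conservative.

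**How often the fallback would be reached.** The unstructured model has 15 covariance parameters for 150–225 subjects. It failed in none of the 36,000 fits.

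**The case against.** The strongest objection is that the branch is almost never reached. No simulated data set triggered the fallback, so the plan's overall Type I error is not shown to exceed 0.05. For the same reason, the CS error rates come from data in which the plan would have used the unstructured model. This stands, and it is why the point is minor.

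The rise in SD is also assumed. The correlation of 0.59 needs equal score SDs at baseline and Week 16. A Week 16/baseline SD ratio of 0.9 would give about 0.83, and a ratio of 1.2 about 0.36. R = 1.0 assumes a score with no measurement noise, which is extreme. At R = 0.7 the excess is small. This stands too: the table shows a range and does not estimate the trial's error rate.

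The SAP could specify a sandwich standard error, which would be compatible with the protocol wording. That is possible. But the protocol itself fixes the fallback structure for the confirmatory test, so the choice is open to review, and both documents should agree.

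The Week 16 ANCOVA on observed data does not use the covariance structure and would expose a discrepancy. As a sensitivity analysis, however, it does not replace the primary p-value. A single prespecified fallback does prevent choosing a structure after seeing the data, and a better-chosen one keeps that advantage. For PPSI there is no confirmatory consequence, because the secondary p-values are not multiplicity-adjusted.

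**Conclusion.** The concern holds, as a conditional and minor one. If the unstructured model fails and residual SDs rise towards Week 16, the fallback's model-based standard error is too small. Type I error per comparison is then roughly 0.06 to 0.13 over the range examined. If the SDs are flat, CS is correct, and if they fall, it is conservative.

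The figures assume model-based standard errors, equal score SDs over time and the decay model above; the protocol has no visit-specific SDs to test these. Since non-convergence is unlikely, the effect on the trial's overall Type I error is probably negligible. The case for a change is that a prespecified fallback should be valid when it is used, and replacing it after unblinding would be a post hoc change to the primary analysis.

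**What to change.** In section 11.3.3 and the Synopsis, replace the fallback with a structure that keeps a separate variance at each visit, for example: *if the unstructured model does not converge, the heterogeneous compound symmetry structure will be used*. Alternatively, keep compound symmetry but state that its standard error will be a robust (sandwich) one, preferably small-sample corrected. The second option can also serve as a last step if the heterogeneous model fails, since its convergence rate was not tabulated here. The PPSI model follows by reference.

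In the same simulations, Type I error was 0.044–0.050 for heterogeneous compound symmetry, 0.049–0.053 for compound symmetry with an ordinary sandwich standard error, and 0.043–0.047 with a corrected one. None of these requires equally spaced visits.

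The cost is one sentence in two places, and nothing changes when the unstructured model converges. If the fallback is used, heterogeneous compound symmetry loses at most about 3% in precision against unstructured (SD of the estimate 1.58 vs 1.53 in the steepest case). Against plain compound symmetry it was about equal in a further set of fits (1.48 vs 1.47).

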11.3.4. Major Secondary Analyses

Major secondary endpoints of this study are not prospectively powered and all p-values reported for secondary endpoints will not adjust for multiple comparisons. Major secondary analyses are:

- The change from baseline in PPSI through Week 16 will be analyzed using the same MMRM model as described for the primary analysis, except for including the baseline PPSI score, instead of baseline PPPASI score, as the covariate. Treatment effects of CNTO 1959 groups versus placebo group will be estimated based on least-square (LS) means of the differences. The p-values for the LS mean differences along with the 2-sided 95% CIs will be presented. The change from baseline in PPSI through Week 16 will also be summarized by treatment group and week using descriptive statistics.
- The proportion of subjects who achieve a PPPASI-50 at Week 16 will be compared between the CNTO 1959 treatment groups and placebo group using a CMH chi-square test stratified by baseline PPPASI total score (≤ 20 , 21-30, ≥ 31) and smoking status (smoking or non-smoking). The proportion through Week 16 will also be summarized by treatment group and week using frequencies and percentages with 95% CI.

11.3.5. Other Efficacy Analyses

For other secondary endpoints (including exploratory endpoints), the continuous variables will be summarized by treatment group and week using descriptive statistics, which will include the number of subjects (N), mean, SD, median, minimum, and maximum and the measurements through Week 16 will be analyzed using an MMRM model where there are repeated measurements; or an analysis of variance model based on appropriate rank scores or ANCOVA model where there is no repeated measurement. The categorical variables will be summarized by treatment group and week using frequencies and percentages. The binary variables through Week 16 will be compared using stratified CMH chi-square test or Fisher's exact test.

Other secondary endpoints are as follows:

- Change from baseline in PPPASI total score over time
- Change from baseline in PPSI total score over time
- Proportion of subjects who achieve a PPPASI-50 over time
- Proportion of subjects who achieve a PPPASI-75, PPPASI-90, PPPASI-100 over time
- Proportion of subjects who achieve a PPSI-50, PPSI-75, PPSI-90, PPSI-100 over time
- Change from baseline in PGA score over time
- Proportion of subjects who achieve a PGA score of cleared (0) or minimal (1) over time
- Proportion of subjects who achieve a PGA score of cleared (0) or minimal (1) and have at least a 2-grade improvement from baseline over time
- Change from baseline in DLQI score over time
- Change from baseline in SF-36 score over time
- Change from baseline in EQ-5D score over time

Exploratory endpoints are as follows:

- Change from baseline in EQ-5D score in PAO subjects over time

11.3.6. Criteria for Endpoints

Primary and major secondary endpoints will be evaluated based on the analyses specified in the efficacy analysis section. The effectiveness of CNTO 1959 treatment in this study will be reached if at least the CNTO 1959 high dose group is shown to be superior to placebo group for the primary efficacy analysis.

11.4. Pharmacokinetic and Immunogenicity Analysis

11.4.1. Analysis Data Set

PK and immunogenicity analyses will be performed based on the population which includes all subjects who received at least 1 administration of CNTO 1959 and have at least 1 observed post-dose PK and immunogenicity data point, respectively, after administration of CNTO 1959.

11.4.2. Pharmacokinetic Analysis

Serum CNTO 1959 concentrations over time will be summarized for each treatment group. Descriptive statistics, including arithmetic mean, SD, median, interquartile range, minimum, and maximum will be calculated at each sampling timepoint. All concentrations below the lowest quantifiable sample concentration of the assay (BQL) or missing data will be labeled as such in the concentration data listing or statistical analysis system (SAS) dataset. The BQL concentrations will be treated as zero in the summary statistics.

If feasible, a population PK analysis using a NONMEM approach will be used to characterize the disposition characteristics of CNTO 1959 in the current study. Data may be combined with those of other selected studies to support a relevant structural model. The CL/F and V/F values will be estimated. The influence of important variables (such as body weight, antibodies to CNTO 1959, and concomitant medications) on the population PK parameter estimates may be evaluated. Details will be given in a population PK analysis plan and the results of the population PK analysis will be presented in a separate technical report.

11.4.3. Immunogenicity Analysis

The incidence and titers of antibodies to CNTO 1959 will be summarized for all subjects who receive at least 1 dose of CNTO 1959 and have appropriate samples for detection of antibodies to CNTO 1959 (ie, subjects with at least 1 sample obtained after their first dose of CNTO 1959). A listing of subjects who are positive for antibodies to CNTO 1959 will be provided in the clinical study report.

If NAbs are measured, the incidence of NAbs to CNTO 1959 will be summarized for subjects who are positive for antibodies to CNTO 1959 and have samples evaluable for NAbs.

11.5. Pharmacokinetic/Pharmacodynamic Analyses

If data permit, the relationships between serum CNTO 1959 concentration and efficacy may be analyzed graphically. If any visual trend is observed, a suitable population PK/PD model may be developed to describe the exposure-response relationship. Details will be given in a population

PK/PD analysis plan, and results of the population PK/PD analysis will be presented in a separate technical report.

11.6. Biomarker Analyses

Biomarker samples will be used to generate serum markers and gene expression for computational analyses.

These analyses are considered exploratory and will be summarized in a separate technical report.

11.7. Safety Analyses

Safety data, including but not limited to, AEs, serious adverse events (SAEs), infections, serious infections, mortality, changes in laboratory assessments, and changes in vital signs through Week 72 will be summarized. Treatment-emergent AEs will be summarized by treatment group and Medical Dictionary for Regulatory Activities (MedDRA) system organ class and preferred terms. Details will be specified in the SAP.

Safety Definitions

Injection Site Reactions

An injection site reaction is any unfavorable or unintended sign that occurs at an injection site and will be recorded as an AE.

Safety Analyses

All safety analyses will be based on the population of subjects who received at least 1 injection of study drug; subjects will be summarized by the treatment they actually received. Routine safety evaluations will be performed. AEs, SAEs, and infections by Week 16 will be summarized by treatment group. Additional summary tables of AEs during the entire treatment period will be generated for all CNTO 1959 treated subjects including those who switched from placebo at Week 16.

The following analyses will also be used to assess the safety of subjects in the study:

- The incidence and type of AEs
- The incidence and type of SAEs
- The incidence and type of infection
- The incidence and type of related AEs
- The incidence and type of injection site reactions
- The laboratory parameters and change from baseline in laboratory parameters (hematology and chemistry)
- The incidence of markedly abnormal laboratory parameters (hematology and chemistry)

Adverse Events

The verbatim terms used in the eCRF by investigators to identify AEs will be coded using the Medical Dictionary for Regulatory Activities (MedDRA). Treatment-emergent AEs are AEs with onset during the treatment phase or that are a consequence of a pre-existing condition that has worsened since baseline. All reported AEs will be included in the analysis. For each AE, the percentage of subjects who experience at least 1 occurrence of the given event will be summarized by treatment group. In addition, comparisons between treatment groups will be provided if appropriate.

Summaries, listings, datasets, or subject narratives may be provided, as appropriate, for those subjects who die, who discontinue treatment due to an AE, or who experience a severe or an SAE. Analysis methods for those AEs reported during after Week 72 visit will be detailed in SAP.

Clinical Laboratory Tests

Laboratory data will be summarized by type of laboratory test (eg, hematology, serum chemistry). National Cancer Institute-Common Terminology Criteria for Adverse Events (NCI-CTCAE) grades (specified in the SAP) will be used in the summary of laboratory data. Descriptive statistics will be calculated for selected laboratory analyses at baseline and at each scheduled time point. A listing of subjects with post-baseline abnormal laboratory results based on CTCAE grades will also be provided.

Electrocardiogram (ECG)

Electrocardiogram data will be summarized by ECG parameter. Descriptive statistics will be calculated at baseline and for observed values and changes from baseline at each scheduled time point. Abnormal findings will also be summarized.

Vital Signs

The observed value and change from baseline of vital signs parameters will be summarized descriptively by visit and treatment group.

Physical Examination

Descriptive statistics of changes from baseline will be summarized at each scheduled time point.

Physical examination findings will be summarized at each scheduled time point. Descriptive statistics will be calculated at baseline and for observed values and changes from baseline at each scheduled time point. Frequency tabulations of the abnormalities will be made.

